While almost all of the reviewed studies of at-risk youth in the meta-analysis and the systematic review were limited by their cross-sectional design, the results do hold promise for mentoring interventions that incorporate the positive characteristics of natural mentors (i.e., more of a friendship-like, ‘coach’, or ‘cheerleader’ role) for young people who have experienced homelessness. These findings are supported by a small ($n = 23$) qualitative study of natural mentoring relationships among homeless youth (ages 14 – 21) that suggests “natural mentors could feasibly serve as a bridge in a coordinated effort to assist youth out of homelessness” (Dang & Miller, 2013, p. 7).

From the limited research that has been done with young people transitioning away from homelessness, the emerging evidence seems to indicate that, while structural supports such as subsidized housing and social service providers are important, these things alone are insufficient to help young people integrate into mainstream society. As it currently stands, it appears as if the burden for achieving meaningful social integration is on the formerly homeless young people, who continue to be marginalized despite achieving stable or semi-stable housing (Quilgars & Pleace, 2016; Thulien et al., 2018). Connecting these young people with an adult who exhibits the relationship-based components of natural mentoring that young people value most (e.g., genuine interest in their well-being and belief in their ability to succeed, a non-judgmental attitude and a willingness to listen, the provision of advice, guidance, affirmation and encouragement) (Dang & Miller, 2013; Thompson et al., 2016; Van Dam et al., 2018) may be key to helping them move forward and integrate into the mainstream.

This intervention will provide 24 young people (ages 16 – 26) who have transitioned out of homelessness and into market rent housing within the past year with rent subsidies for 24 months. Half of the young people will also receive mentorship. We chose to focus on young people living in market rent housing because, due to limited subsidized housing options, this is the reality for most young people exiting homelessness.

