Initially, we proposed to our community partners a study design where only half the young people would receive rent subsidies, with the other half receiving ‘treatment as usual’; however, we abandoned this idea after our community partners challenged the ethics of not providing or delaying rent subsidies for young people living a precarious existence and desperate for immediate, tangible support to help them remain in market rent housing. Consequently, we adopted the stance that, given housing is a basic human right², we would offer rent subsidies to *all* of the study participants. While this does move us away from the ‘gold standard’ in terms of measuring the impact of rent subsidies on social integration, we believe the mixed methods longitudinal design will still yield important insights in this regard. Moreover, this design adaptation reflects our deep commitment to engage in community-based participatory action research (CBPAR) – a methodology that challenges traditional epistemological assumptions of what constitutes ‘good’ evidence, demands researcher humility, stresses genuine and equitable academic-community partnerships, and facilitates the undertaking of research in a way that the *community* feels is most beneficial to their members

² “Adequate housing is essential to one’s sense of dignity, safety, inclusion and ability to contribute to the fabric of our neighbourhoods and societies...without appropriate housing it is often not possible to get and keep employment, to recover from mental illness or other disabilities, to integrate into the community, to escape physical or emotional violence or to keep custody of children” (Ontario Human Rights Commission, n.d.).

(Goodkind et al., 2017; Wallerstein & Duran, 2006; Wallerstein, Duran, Oetzel, & Minkler, 2018).

Half of the young people will be randomized to receive regular mentorship from an adult mentor, tasked with helping their mentee bridge the gap between homelessness and mainstream living. While some of these mentors will not be ‘natural’ in the sense that these may not be pre-existing, organically-formed relationships (see 3a. Mentorship), the mentors will incorporate the key relationship-based components of natural mentoring mentioned previously, with a strong emphasis on a strengths-based approach (i.e., focus on the young person’s strengths as opposed to their limitations) and the connection of participants to larger social networks (including education and employment).

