Findings from this longitudinal pilot randomized controlled trial will help address the gap in our knowledge about the impact of financial support and mentorship on meaningful social integration for young people who have experienced homelessness and are living in market rent housing.

2. Study Aim and Objectives

The overarching aim of this mixed methods study is to assess whether and how rent subsidies and mentorship influence social integration outcomes for formerly homeless young people living in market rent housing in three urban settings.

Specifically, the objectives of this study are to:

1. Determine whether rent subsidies plus mentorship results in better social integration outcomes than only receiving rent subsidies with respect to: a) community integration (psychological and physical); and b) self-esteem at our primary endpoint of 18 months.
2. Determine whether rent subsidies plus mentorship results in better social integration outcomes than only receiving rent subsidies with respect to: a) social connectedness; b) hope; and c) sustained academic and vocational participation at our secondary endpoint of 18 months.
3. Explore whether rent subsidies plus mentorship results in better social integration outcomes than only receiving rent subsidies with respect to: a) income; b) perceived housing quality; c) psychiatric symptoms; and d) sense of engulfment at our exploratory endpoint of 18 months.
4. Integrate qualitative data to facilitate a fuller understanding of the quantitative data and deepen our understanding of what the study participants (young people and mentors) found most beneficial about the intervention and how it could be improved.

3. Study Design

This study will employ a convergent mixed methods design (i.e., quantitative and qualitative data are collected concurrently, and the findings combined) embedded within a RCT and a CBPAR framework (Creswell, 2014; Creswell & Plano Clark, 2018). We believe a mixed methods RCT is appropriate given the complex explanatory pathways (i.e., social and behavioral processes that may act independently and interdependently) of this intervention (Lewin, Glenton, & Oxman, 2009). In addition, the qualitative data will provide insights on contextual factors that may impact the external validity of our findings (Goodkind et al., 2017). Most importantly, this design provides a crucial (and underutilized) youth-informed perspective on social integration.

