All of the study participants will be screened for eligibility (see criteria above) and recommended for the study by one of our community partners (Covenant House Toronto, Living Rock Ministries, and The RAFT). A member of the research team will call each recruited youth on the telephone and arrange to meet them at a location most convenient for the youth. Potential participants will be given a copy of the participant information and consent form to read. This document will also be reviewed verbally to ensure that those who have low literacy levels have been given the information required to give informed consent. During this process, the research team member will assess the capacity of the potential participant to provide free and informed consent. If it is unclear whether a youth is able to provide consent, the study co-investigator ([name]) will be contacted immediately. [name] will arrange for a qualified member of the research team to conduct a capacity assessment. If it is determined that a youth is not able to consent, they will be informed of this and they will be excluded from the study. The appropriate community partner will be notified as well.

3f. Allocation Procedure

[figure not shown]
If the participant meets the eligibility criteria, informed consent will be obtained, and the participant will be enrolled in the study. During this initial meeting, enrolled participants will participate in a baseline interview. There will be no unmasking of assignment prior to randomization. Following the baseline interview, participants at each of the three study sites (Toronto (n=12), Hamilton (n=6), and St. Catharine's (n=6)) will be randomized using block randomization to either the intervention (rent subsidies plus mentoring) or control (rent subsidies only) group. Randomization will be balanced by site based on random block sizes of two and four. The advantage of using block randomization is to uniformly distribute participants into treatment groups within each site (Efird, 2010). Because small block sizes may increase the risk of guessing the allocation procedure and subsequently introducing bias into the enrolment procedure, random block sizes will be used to avoid this potential selection bias (Suresh, 2011).

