1. We will observe better mean scores (community integration and self-esteem) in the participants who receive rent subsidies plus mentorship (intervention group) compared to the participants who receive rent subsidies only (control group) by our **primary endpoint of 18 months** of study participation.

We hypothesise that, for the **secondary outcome** measures of social connectedness, hope, and academic and vocational participation:

1. We will observe better mean scores (social connectedness and hope) in the intervention group relative to participants in the control group by our **secondary endpoint of 18 months** of study participation.
2. Participants in the intervention group will be more likely than the control group to demonstrate sustained engagement in academic and vocational activities (education, employment, and/or skills training) by our **secondary endpoint of 18 months** of study participation.

4c. Quantitative Measures

Quantitative data (Appendix A – Quantitative Data Collection) will be collected at **six points** in time over the course of 30 months: baseline, month six, month 12, month 18, month 24, and month 30. **Nine instruments** (Table 2) will be employed to assess the outcome variables. We have purposely chosen instruments utilized in previous research with young people who have experienced homelessness (e.g., Kidd et al., 2016; Kozloff et al., 2016; McCay et al., 2015) so that meaningful comparisons can be made across studies (Moore et al., 2015) in this nascent area of research. One instrument we do not believe has been used with this population is the Modified Engulfment Scale (McCay & Seeman, 1998). We have included engulfment as an exploratory outcome given the emerging qualitative evidence on the crucial role of identity (self-concept) in a young person's transition away from homelessness (Brueckner et al., 2011; Karabanow et al., 2016; Thulien et al., 2018).

Table 2. Quantitative Instruments

Instrument	Psychometric Information
Beck Hopelessness Scale (Beck, Weissman, Lester, & Trexler, 1974).	This 20-item scale measures motivation, expectations, and feelings about the future (internal consistency $\alpha = .93$).

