At baseline, twelve participants (six from each arm of the study) will be invited to participate in **six semi-structured individual interviews**, which will take place at the same time as the quantitative data collection: **baseline, month six, month 12, month 18, month 24, and month 30**. Participants will be purposively selected with a goal of having input from each of the three communities and a fairly equal gender and ethno-racial representation.

All of the mentors ($n = 12$) will be invited to participate in **two focus groups**, which will take place at **month 12 and month 24**.

The questions posed during the semi-structured interviews and focus groups will be guided by the study objectives, but will be conversational and exploratory in nature with particular attention to understanding *how* mentoring and/or rent subsidies influence social integration outcomes for formerly homeless young people living in market rent housing. Given the emergent nature of qualitative inquiry (Denzin & Lincoln, 2011; Eakin & Mykhalovskiy, 2003), we expect the interview and focus group questions to evolve over time as key preliminary themes begin to surface. It is anticipated that the individual interviews (including quantitative data collection, which will consistently take place first) will last approximately 60 – 75 minutes, and the focus

groups approximately 60 – 90 minutes. The individual interviews and the focus groups will be conducted by [name] at locations most convenient for those participating. To get a better sense of each young person’s living situation and to minimize researcher – participant power imbalance (Israel et al., 2018), [name] will suggest that the individual interviews take place in or nearby the young people’s homes. The individual interviews and focus groups will be audio recorded and transcribed verbatim.

4e. Honoraria

All of the study participants will be paid an honorarium of \$20 at each of the six quantitative data collection points. Those participating in semi-structured interviews will be paid an additional \$30 at each interview. This amount was based on the co-investigator’s previous experience with this population and after consulting with our community partners.

5. Data Analysis

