One major critique of mixed methods RCTs is that, typically, there is no true integration (i.e., ‘mixing’) of quantitative and qualitative findings at the level of analysis or interpretation (Lewin, Glenton, & Oxman, 2009). Moreover, it is often unclear whether or how the quantitative and qualitative researchers have worked together to maximize the potential synergies between these different approaches (Lewin et al.). With this in mind, our study team, consisting of researchers with quantitative and qualitative expertise, worked together to develop this study protocol and anticipate meeting quarterly to discuss the emerging analysis and to explore (and follow up on) similarities or discrepancies between the quantitative and qualitative data.

5a. Quantitative Data

All analyses will be performed using the intention-to-treat principle; that is, all participants will be included and analyzed in the groups they were originally randomized. Baseline characteristics of the intervention and control groups will be summarized using descriptive statistics (i.e., mean, standard deviation, median and interquartile range for continuous variables, and frequencies and proportions for categorical variables). We will also calculate descriptive statistics for outcomes at each study time point, and will explore differences in trajectories from baseline to 30 months follow-up between intervention and control groups using scatterplots and box-plots. Differences with 95% confidence intervals in continuous outcomes at 18 months (psychological community integration, self-esteem, social connectedness, hope, perceived housing quality, psychiatric symptoms, and sense of engulfment) between participants who received rent subsidies plus mentorship and participants who only received rent subsidies will be estimated using Analysis of Covariance (i.e., linear regression models), including an indicator of intervention group and the baseline value of the outcome. We will perform regression diagnostics and will repeat analyses using the non-parametric Wilcoxon

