This study has a number of limitations. First, the young people recruited for this pilot study will be a small sample of youth connected to urban-based social service providers in the province of Ontario. Thus, the findings may not be generalizable to formerly homeless young people living in other contexts and/or not connected to social service agencies. Second, the quantitative instruments are based on self-report and may

involve a degree of response bias. Finally, the quantitative measures we have chosen are what we believe to be surrogate markers of meaningful social integration. Future work will likely be needed to more accurately capture this complex concept.

9. Significance

This pilot RCT study will be the first to test the impact of economic and social supports on meaningful social integration for formerly homeless young people living in market rent housing. We believe the mixed methods design will illuminate important contextual factors that must be considered if the intervention is to be scaled up and replicated elsewhere. Importantly, the CBPAR framework will incorporate the perspectives of the community, including formerly homeless young people, who are in the best position to determine what might work best in the context of their lives.

References

Altena, A. M., Brilleslijper-Kater, S. N., & Wolf, J. R. (2010). Effective interventions for homeless youth: A systematic review. *American Journal of Preventive Medicine*, 38(6), 637-645. doi: 10.1016/j.amepre.2010.02.017.

Beck, A. T., Weissman, A., Lester, D., & Trexler, L. (1974). The measurement of pessimism: The hopelessness scale. *Journal of Consulting and Clinical Psychology*, 41(6), 639-660. doi: [10.1037/h0037562](https://doi.org/10.1037/h0037562).

Chenail, R. J., St. Goerge, S., Wulff, D., & Cooper, R. (2012). Action research: The methodologies. In P. L. Munhall (Ed.), *Nursing research: A qualitative perspective* (5th ed.) (pp. 455-470). Sudbury, MS: Jones & Bartlett.

Ciarolo, J. A., Edwards, D. W., Kiresuk, T. J., Newman, F. L., & Brown, T. R. (1981). *Colorado symptom index*. Washington, DC: National Institute of Mental Health.

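### Does the Significance section promise a randomised test of rent subsidies that the design cannot deliver?

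*Combined protocol and SAP*

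**What the plan says.** Section 9 describes the trial in one sweep: "This pilot RCT study will be the first to test the impact of economic and social supports on meaningful social integration". Section 2 gives the overarching aim of the mixed methods study as to "assess whether and how rent subsidies and mentorship influence social integration outcomes". The last sentence of section 1 is similar: it expects the findings of the pilot randomised trial to inform the impact of both financial support and mentorship.

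The design is narrower. Sections 1 and 3 give the subsidy to all 24 participants for 24 months, and section 1 adds: "Half of the young people will also receive mentorship". Under section 3f, participants "will be randomized using block randomization to either the intervention (rent subsidies plus mentoring) or control (rent subsidies only) group". The monthly amount is $500 in Toronto and $400 in Hamilton and St. Catharines (section 3, footnote 3).

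Section 1 also explains how this came about. An unsubsidised comparison group was proposed first and was dropped after the community partners challenged its ethics. The authors accept that they thereby give up the strongest design "in terms of measuring the impact of rent subsidies on social integration, we believe the mixed methods longitudinal design will still yield important insights".

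**The concern.** A reader who goes straight to section 9 would expect a randomised answer on two things, the economic support and the social support. The design can answer only one of them: what mentorship adds for young people who already have a subsidy. The combined package is not tested either, because the control group receives the economic half of it.

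Section 8 lists three limitations (a small, service-connected sample; self-report; surrogate measures), and none mentions the missing subsidy comparison. The caution at the end of the quantitative part of section 5a concerns small numbers, and a larger trial with the same two arms would have the same gap. If both arms improved over time, loose wording could lead someone to credit the subsidy with the authority of a randomised trial.

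**Working it through.** The plan states no power or sample-size figure that bears on this point, so the check is whether a subsidy effect can be estimated and whether any planned analysis claims to estimate one.

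**Inputs.** Site sizes are 12, 6 and 6 (section 3f), and 12 + 6 + 6 = 24, which agrees with the stated total. There are 12 participants in the mentored arm (section 3a), leaving 24 − 12 = 12 controls. The subsidy lasts 24 months (section 3) and the endpoint is 18 months (sections 2 and 4b).

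**Is there a subsidy contrast between arms?** Because 18 is less than 24, everyone is planned to be subsidised at the endpoint: 12/12 − 12/12 = 0.

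**Could the planned model estimate one?** The section 5a model for continuous outcomes is: outcome at 18 months = b0 + b1 × group + b2 × baseline. It has three columns and rank 3, so the mentorship effect b1 is estimable. A subsidy indicator equals 1 for everyone and so duplicates the intercept: four columns, rank still 3. The dollar amount is no help, since amount = 400 + 100 × (Toronto), which is fixed by city. Adding two city indicators and the amount to the model gives six columns and rank 5. These results restate the design. They reveal no error in it.

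**Could change over time estimate one?** Measurements are taken "in time over the course of 30 months: baseline, month six, month 12, month 18, month 24, and month 30". Assume that the subsidy starts after the baseline interview and stops at month 24; the start relative to baseline is not stated. Its status then changes at the same visits for everyone and cannot be separated from time. Before-and-after change can be described, but it cannot be attributed to the subsidy.

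**Does anything planned claim a subsidy effect?**

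- Objectives 1 to 3 (section 2): all three compare subsidy plus mentorship with subsidy alone.
- Hypotheses (section 4b): one primary and two secondary, 1 + 2 = 3, all between the randomised arms.
- 18-month comparisons (section 5a): 7 continuous outcomes + 1 count outcome + 2 binary outcomes = 10, all between arms. For the continuous outcomes the plan says that differences "between participants who received rent subsidies plus mentorship and participants who only received rent subsidies will be estimated using Analysis of Covariance".
- Trajectory plots to month 30 (section 5a): descriptive, and drawn between the two arms.

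Subsidy effects claimed: 0 of 3 objectives, 0 of 3 hypotheses and 0 of 10 comparisons.

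**Where are subsidies taken up?** In the descriptive summaries at each visit, and in the interviews and focus groups, which ask how "mentoring and/or rent subsidies influence social integration outcomes for formerly homeless young people" (section 4d). That is the longitudinal mixed methods evidence section 1 offers, and it suits the question of how.

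**The case for a change.** The strongest case for an edit is that it would be cheap and accurate. One sentence in section 9 could confine the randomised test to mentorship added to a subsidy, and one in section 8 could repeat the caveat from section 1. Readers of a Significance section may not go back to the rationale, and dissemination is to reach community as well as academic audiences, including through a film about the impact of both supports (section 7a). The verb in section 9 is also stronger than what section 1 offers: a test in one place, insights in the other.

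The point about wording stands: section 9 is looser than the design, the closing sentence of section 1 shares the fault, and section 8 is silent. The consequence does not follow. The objectives, hypotheses and section 5a determine what will be estimated and concluded, and they are framed correctly. The aim in section 2 belongs to the mixed methods study as a whole. Objectives 1 to 3 directly below it state the randomised contrast, and objective 4 gives the qualitative data their role, so that section does not mislead when read through. The disclosure in section 1 is explicit, gives its reason, and comes before the aim. Section 5a further limits all results to generating data and hypotheses for a larger trial.

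**Conclusion.** The concern is right about the wording, but it does not call for a change to the plan. The randomised contrast for the subsidy is zero by design. That was a deliberate trade-off, made on ethical grounds with the community partners and disclosed in section 1, and no planned analysis tries to recover a subsidy effect. What remains is a broad phrase in a narrative section and a caveat that is not repeated in section 8. Correcting either would leave every endpoint, estimator, sample size and result as it is.

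This rests on the planned schedule, with everyone subsidised through month 18, and on the report keeping to the contrasts in sections 2, 4b and 5a. The assumption about when the subsidy starts matters only to the remark on change over time. The conclusion about the randomised arms does not depend on it.
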